9.1.2. Treatment-Emergent Adverse Events

The incidence of TEAEs will be presented by system organ class, preferred term, and dose level for the BIVV001 Treatment Period and separately for the Advate Treatment Period. In addition, the incidence of TEAEs will be presented by preferred term in descending order of incidence. In these summaries, adverse events that occur during pre-study FVIII product use will be summarized in the BIVV Treatment Period as well as in a separate summary. At each level of patient summarization, a patient is counted once if the patient reported one or more events. Percentages will be based on the number of patients at each dose level for the Safety Analysis Set.

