3. STUDY DESIGN

3.1. Overall Study Design

[figure not shown]
This is a Phase 1/2a, open-label, dose-escalation, multicenter study designed to evaluate the safety, tolerability, and PK of a single IV dose of BIVV001 in subjects with severe hemophilia A who have received at least 150 exposure days of prior FVIII treatment.

Approximately 18 male PTPs aged 18 to 65 years will be enrolled: approximately 8 subjects in the low-dose cohort (Advate 25 IU/kg and BIVV001 25 IU/kg) and approximately 10 subjects in a high-dose cohort (Advate 65 IU/kg and BIVV001 65 IU/kg).

Each subject will be dosed with Advate followed by a PK sampling period. Following a brief washout period, each subject will then be administered BIVV001 followed by a PK sampling period. Subjects will undergo safety observation for 28 days following the injection of BIVV001, including sample collection for inhibitor assessments 14 and 28 days after the injection of BIVV001. Subjects may resume treatment with their pre-study FVIII product during the 28-day observation period after completing Visit 14 activities (which include the 14-day inhibitor test). Only subjects with adequate samples for PK and inhibitor characterization following both Advate and BIVV001 dosing will be considered evaluable; additional subjects will be enrolled as needed to ensure that at least 6 subjects in the low-dose cohort and 8 subjects in the high-dose cohort provide evaluable PK and inhibitor data.

An independent Data Safety Monitoring Committee (DSMC) will evaluate the safety data from the study on an ongoing basis.

Figure 1: Study Schema

* Screening may be extended up to 120 days with prior Sponsor approval. If the Screening Period extends beyond 56 days, screening assessments must be repeated as specified in the protocol prior to dosing with Advate. Washout duration at least 96 hours (4 days) from the most recent FVIII dose (prestudy FVIII) for a conventional product, 120 hours (5 days) for an extended half-life FVIII product.

[figure not shown]
** Washout duration at least 72 hours (3 days) from the Advate dose for the BIVV001 low-dose cohort, and at least 96 hours (4 days) for the BIVV001 high-dose cohort.

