3.5. Interim Analysis

No formal interim analyses are planned.

At least one interim analysis will be performed when at least 3 subjects in the low dose cohort have completed the 28-day safety observation period and have available safety and PK data.

This analysis will focus on baseline demographic information, adverse events, and pharmacokinetic data and will be of a descriptive nature. No formal hypothesis testing will be performed.

The DSMC will review safety summaries and listings on a quarterly interval as well as on an ad hoc basis, as needed. In addition, the DSMC will evaluate available data following the low dose cohort to determine the appropriateness of escalating to the high dose cohort once the following conditions have been met: a) inhibitor test results from samples collected 14 days after the BIVV001 injection are available for at least 6 of the 8 subjects in the low-dose cohort, and b) adequate PK sampling following the BIVV001 dose has been completed and safety assessment results through the end of PK sampling are available for all active subjects in the low-dose cohort. Further details are provided in the DSMC charter.

Other descriptive interim analyses may be performed as necessary to support dose regimen planning for future studies.

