4.2. Safety Analysis Set

The Safety Analysis Set is defined as all subjects who receive at least one dose of Advate or BIVV001.

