5.1.1.5. Safety Observation Period During BIVV001 Treatment

The safety observation period during BIVV001 treatment starts at the single dose administration of BIVV001 and ends at the 28-day visit or time of early withdrawal. Subjects may resume treatment with their pre-study FVIII product during the 28-day safety observation period after completing Visit 14 activities (which include the 14-day inhibitor test).

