6. STUDY POPULATION

6.1. Disposition of Subjects

Subject disposition will be summarized for each dose level and overall using the All-Enrolled Analysis Set. The table will present the number and percentage of subjects in the Safety Analysis Set and the PK Analysis Set. In addition, the number of subjects who completed the study and the number of subjects who discontinued from the study early, including the primary reason for discontinuation, will be tabulated.

Subject disposition, including date of last visit and reason for early discontinuation, for subjects who did not complete the study, will be provided in a listing.

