9.1. Adverse Events

Adverse events will be classified using the Medical Dictionary for Regulatory Activities (MedDRA) System Organ Classes and Preferred Terms (Version 20.0 or later). Any AE experienced by the subject from the day of signing the Informed Consent Form until 28 days after BIVV001 administration will be recorded on the eCRF, regardless of the severity of the event or its relationship to study treatment.

A treatment-emergent AE (TEAE) is defined as any adverse event that begins on or after the study treatment (Advate or BIVV001) and within 28 days after BIVV001 administration. AEs with missing start dates will be assumed to be treatment-emergent, unless the stop date is before the dosing date. An AE starting on or after the single dose of study-administered Advate but before the single dose of study-administered BIVV001 will be counted in the Advate Treatment Period. An AE starting on or after the single administration of study-administered BIVV001 and up to the end of study will be counted in the BIVV001 Treatment Period. During the BIVV001 Treatment Period, subjects may resume treatment with their pre-study FVIII product after completing Visit 14 activities. Adverse events that occur during pre-study FVIII product use will be summarized in the BIVV Treatment Period summaries as well as in a separate summary. Adverse events that occur during a major surgical period will be listed separately and will not be included in the AE summary tables.

In general, AEs will be summarized by subject incidence by dose level and overall for the BIVV001 Treatment Period and separately for the Advate Treatment Period. In addition, all AEs will be presented in a data listing by dose level and subject. In this listing, AEs that occur prior to study treatment and AEs that occur during a major surgical period will be flagged.

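### BIVV001-period adverse event percentages divide by everyone in the cohort given either drug, so a subject given only Advate dilutes the BIVV001 rate

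*SAP*

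**What the plan says.** Section 9.1.2 of the SAP presents TEAE incidence for the BIVV001 Treatment Period and, separately, for the Advate Treatment Period. One sentence sets the denominator for both: "Percentages will be based on the number of patients at each dose level for the Safety Analysis Set". Section 4.2 defines that set as "all subjects who receive at least one dose of Advate or BIVV001", and Section 9 uses it for every safety analysis.

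The numerator depends on the period. For the BIVV001 tables, Section 9.1 gives this rule: "An AE starting on or after the single administration of study-administered BIVV001 and up to the end of study will be counted". Events between the two doses belong to the Advate period.

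Dose level works as a cohort label. Section 3.1 describes "approximately 8 subjects in the low-dose cohort (Advate 25 IU/kg and BIVV001 25 IU/kg"), so one label covers both drugs. Section 6.1 applies the same label to people who may not have been dosed at all: "Subject disposition will be summarized for each dose level and overall using the All-Enrolled Analysis Set".

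Sections 9.1 and 9.1.2 also announce a separate summary of events during pre-study FVIII use. Section 5.1.1.5 makes that use optional: "Subjects may resume treatment with their pre-study FVIII product during the 28-day safety observation period after completing Visit 14 activities". Section 5.1.1.6 starts the period only at the first resumed dose.

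**The concern.** Numerator and denominator refer to different groups. Dosing is sequential, Advate first and BIVV001 after a washout (Section 3.1). Someone who has had only the first dose is in the Safety Analysis Set and in the cohort, but cannot have an event that counts in the BIVV001 period. Each such subject lowers the BIVV001 percentage and none can raise it.

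This can arise in two ways. A subject may leave between doses, or may still be between doses when data are cut. Section 3.5 plans a descriptive interim analysis that includes adverse events "when at least 3 subjects in the low dose cohort have completed the 28-day safety observation period", and also states: "The DSMC will review safety summaries and listings on a quarterly interval".

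The occurrence of adverse events is a primary endpoint of this first-in-human study (Section 2.2.1). In cohorts of 8 and 10, one subject moves a percentage visibly, and the shift is always in the direction that flatters the new product. The pre-study FVIII summary has the same weakness for a different reason: subjects who never resumed were never at risk in that period.

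**Working it through.** There is no power calculation or stated percentage to reproduce. The one arithmetic check available agrees: 8 + 10 = 18 planned subjects (Section 3.1).

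**Inputs from the SAP.** Planned cohort sizes N = 8 (low dose) and N = 10 (high dose), 18 overall; the denominator rule in Section 9.1.2; set membership in Section 4.2; the numerator rule in Section 9.1.

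**Assumed inputs.** The number a of subjects given Advate but not BIVV001, the number x with an event, and the number who resume pre-study product. The SAP gives none of these, so ranges are shown.

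**Formulas.**
- Reported BIVV001 incidence = x/N
- Incidence among those at risk = x/(N − a)
- Reported ÷ at-risk = (N − a)/N, so the relative understatement is a/N, whatever x is (x ≥ 1)

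**Relative understatement, a/N.**

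| a | N = 8 | N = 10 | N = 18 |
|---|---|---|---|
| 0 | 0% | 0% | 0% |
| 1 | 12.5% | 10.0% | 5.6% |
| 2 | 25.0% | 20.0% | 11.1% |
| 3 | 37.5% | 30.0% | 16.7% |

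**Example at the final analysis.** N = 8, a = 1, x = 2: the at-risk rate is 2/7 = 28.6% and the reported rate is 2/8 = 25.0%, a ratio of 0.875.

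**Early data cut** (assumed: 3 subjects given BIVV001, one affected).
- No further subject between doses: 1/3 = 33.3% reported, which is correct
- One further subject: 1/4 = 25.0% reported against 33.3%
- Two further subjects: 1/5 = 20.0% reported against 33.3%

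**Pre-study FVIII summary** (low-dose cohort of 8, one affected, Section 9.1.2 denominator applied). The reported figure is always 1/8 = 12.5%. The at-risk figure is 1/8 = 12.5% if all 8 resumed, 1/6 = 16.7% if 6 did and 1/4 = 25.0% if 4 did.

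**Does another section repair this?** Section 5.2.2 has a default denominator based on non-missing data, but it gives way where another rule is stated, and Section 9.1.2 states one. Section 5.1 calls for summaries by study drug and dose level; that governs layout and sets no denominator. No section limits the BIVV001-period denominator to subjects dosed with BIVV001.

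**The case against.** **Dose level is undefined and could mean the dose of BIVV001 received.** Section 8.1 does speak of subjects given the low dose of BIVV001. But Sections 3.1, 6.1 and 6.2.1 use dose level for the cohort, and Sections 9.2.1, 9.2.3, 9.2.4 and 9.4 add the word drug when they group by drug. Section 9.1.2 does not. The cohort reading is much the stronger.

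**The sentence stands only in Section 9.1.2.** Sections 9.1.1 and 9.1.3 to 9.1.5 have no denominator sentence, so the Section 5.2.2 default may apply there. This is fair: strictly, the wrong rule is written only for the tables in Section 9.1.2. The default does not clearly help the others, though, because having no adverse event recorded is not a missing value. One rule for all the Section 9.1 tables is safer.

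**The interim scenario is assumed.** Sections 3.5 and 10 could be read as limiting the interim analysis to completers, all of whom had BIVV001. For the escalation decision, Section 3.5 requires post-BIVV001 sampling to be complete for all active low-dose subjects, so only a dropout could then be Advate-only. DSMC details are left to a charter not seen here. These points stand, and the early-cut figures are illustrations only.

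**The effect may be nil and can be detected.** No hypothesis is tested (Section 3.2), counts accompany the percentages, and by-subject listings of events and dosing are planned. A reader could rebuild the rate. That limits the harm but does not make the stated percentage right.

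**The pre-study FVIII summary might show counts only.** It is absent from the table list in Section 12.1, so its format is open. But it is announced in the section that the percentage sentence governs, and the dilution follows if that sentence is applied.

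**Conclusion.** The concern holds. As written, the Section 9.1.2 denominator understates BIVV001 Treatment Period incidence by a/N whenever a subjects have had Advate but not BIVV001 and at least one event occurs. For a single such subject that is 12.5%, 10.0% or 5.6% in relative terms (low dose, high dose, overall); one in each cohort gives 2/18 = 11.1% overall.

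This rests on the cohort reading of dose level and on assumed values of a. If every Advate-dosed subject goes on to BIVV001, the BIVV001 tables are unaffected. The pre-study FVIII point does not depend on Advate-only subjects: it needs only that some subjects do not resume and that percentages are shown on the Section 9.1.2 base. The matter should be corrected because it concerns a primary-endpoint summary, but it threatens no test or stated decision rule.

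**What to change.** In Section 9.1, replace the single denominator sentence with one per period, applied to all the Section 9.1 TEAE tables and to interim and DSMC cuts:

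- BIVV001 Treatment Period: Safety Analysis Set subjects in the cohort who received BIVV001.
- Advate Treatment Period: Safety Analysis Set subjects in the cohort who received Advate.
- Separate pre-study FVIII summary: subjects who took at least one dose of pre-study product in the period defined in Section 5.1.1.6.

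The inhibitor and antibody tables can stay on the Section 5.2.2 default.

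The cost is a few lines of SAP text and one flag per period. Some reported percentages will be slightly higher, and N may differ between the period tables, so each table should show its own N. Study conduct does not change.

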9.1.3. Severity of Adverse Events

The severity of AEs will be recorded on the AE form as “Mild”, “Moderate”, or “Severe”. A summary of TEAEs by system organ class, preferred term, dose level, and severity will be presented for the BIVV001 Treatment Period and separately for the Advate Treatment Period.

In addition, all severe adverse events will be presented in data listings by dose level and subject.

9.1.4. Relationship of Adverse Events to Study Drug

Treatment-emergent AEs will be classified by relationship to study drug as “Not Related”, “Related to Advate”, or “Related to BIVV001”. A summary of related TEAEs by system organ class, preferred term, and dose level will be presented for the BIVV001 Treatment Period and separately for the Advate Treatment Period.

In addition, all related adverse events will be presented in data listings by dose level and subject.

9.1.5. Serious Adverse Events

Any AE reported as resulting in death, immediate risk of death (life threatening), inpatient hospitalization or prolongation of existing hospitalization, persistent or significant disability/incapacity, or a congenital/anomaly/birth defect will be classified as serious adverse event (SAE). An SAE may also be any other medically important event that, in the opinion of the Investigator, may jeopardize the patient or may require intervention to prevent one of the other outcomes listed above.

A summary of treatment-emergent SAEs by system organ class, preferred term, and dose level will be presented for the BIVV001 Treatment Period and separately for the Advate Treatment Period.

In addition, all SAEs will be presented in data listings by dose level and subject.

9.1.6. Adverse Events Leading to Study Withdrawal

All AEs reported on the AE form with the question “Was the subject terminated from study due to this AE” answered “Yes” will be presented in data listings by dose level and subject.

9.1.7. Death

All patient deaths during the study will be recorded on the Death form and will be presented in data listings by dose level and subject.

9.2. Clinical Laboratory Evaluations

The following protocol required laboratory tests will be performed:

- Hematology: red blood cell count, white blood cell count and differential, platelet count, hemoglobin, and hematocrit
- Clinical chemistry: ALT; AST; alkaline phosphatase; gamma-glutamyl transferase; bilirubin; blood urea nitrogen; creatinine; glucose; total protein; sodium; potassium; and chloride

- Urinalysis: specific gravity; pH; color; appearance; leukocyte esterase; protein; glucose; ketones; occult blood; bilirubin; urobilinogen; nitrite; and microscopic examination of urine sediment
- Coagulation and thrombosis markers: prothrombin time (PT); aPTT; d-dimer; international normalized ratio; thrombin anti thrombin complex; prothrombin fragment 1.2; and the von Willebrand comprehensive panel (which includes assessments of FVIII activity, VWF ristocetin cofactor activity, and VWF antigen)
- [REDACTED]
- [REDACTED]
- Detection of FVIII inhibitors, as determined by the Nijmegen modified Bethesda assay. A subject's blood will be considered to be positive for FVIII inhibitor when an initial test result of ≥ 0.6 BU/mL is identified and confirmed by a subsequent test result from an independent blood sample collected within 2 to 4 weeks of the first positive sample.

Refer to Section 5 of the protocol for the timing of assessments.

Laboratory assessments taken during the surgery period will be listed only and will not be included in the laboratory data summaries.

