9.2.4. Inhibitor Development using the Nijmegen-modified Bethesda Assay

An inhibitor assessment using the Nijmegen-modified Bethesda assay will be performed for all subjects at Screening, Visit 2 (pre-injection for Advate), Visit 6 (pre-injection for BIVV001), Visit 14 (14 days post-injection for BIVV001) and the End of Study/Early Termination Visit.

The number and percentage of subjects who test positive for inhibitor will be presented for each drug by dose level. In addition, inhibitor status will be presented by dose level and subject in a listing using the Safety Analysis Set.

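### Does the SAP lose an inhibitor confirmed after the last listed visit, or misreport an initial positive that is never retested?

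*SAP*

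**What the plan says.** Section 9.2 holds the only definition of a positive inhibitor. An initial Nijmegen-modified Bethesda result of at least 0.6 BU/mL must be "confirmed by a subsequent test result from an independent blood sample collected within 2 to 4 weeks of the first positive sample". For scheduling, the same section says "Refer to Section 5 of the protocol for the timing of assessments".

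Section 9.2.4 lists samples at Screening, before Advate (Visit 2), before BIVV001 (Visit 6), and then at "Visit 14 (14 days post-injection for BIVV001) and the End of Study/Early Termination Visit". Section 3.1 fixes the nominal days, "including sample collection for inhibitor assessments 14 and 28 days after the injection of BIVV001". Under Section 5.1.1.5 the BIVV001 observation period "ends at the 28-day visit or time of early withdrawal".

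Two outputs are planned in Section 9.2.4: "The number and percentage of subjects who test positive for inhibitor will be presented for each drug by dose level", and "inhibitor status will be presented by dose level and subject in a listing using the Safety Analysis Set".

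Three general rules bear on this:

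- Section 5.1 leaves unscheduled-visit data out of analyses unless the SAP specifies something else, but lists them.
- Section 5.1.1.10 gives unscheduled visits no visit assignment in summary tables.
- Section 5.2.2 takes percentages over subjects with non-missing data for the summary concerned, and prints no percentage for a zero count.

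**The concern.** Section 2.2.1 names inhibitor development in the primary endpoint, and each cohort has only about 8 or 10 subjects, so the status of one subject matters. A positive needs two samples at least two weeks apart, yet no sample is listed after the 28-day visit. A confirming sample drawn later could be labelled unscheduled and, on a literal reading of Section 5.1, left out. Section 9.2.4 does not say that it counts.

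There is also no category for a subject whose initial result reaches the threshold but who has no valid retest. Such a subject would not appear in the positive count. The summary table could then show zero inhibitors in a cohort where one subject had a result at or above 0.6 BU/mL, and a reader of the table alone would not know.

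**Working it through.** The SAP gives no figure to reproduce here. The check is date arithmetic, a reading of the rules against each other, and the size of one subject.

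**1. Retest windows** (days after the BIVV001 injection; window = day of first positive + 14 to + 28)

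| First positive | Window | Listed sample inside it |
|---|---|---|
| Day 14 | 14 + 14 = 28 to 14 + 28 = 42 | Day 28, exactly at the lower limit |
| Day 28 | 28 + 14 = 42 to 28 + 28 = 56 | None |
| Early termination | 14 to 28 days after that visit | None |

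At nominal timing a 14-day positive is confirmable at the 28-day visit (28 − 14 = 14 days). A draw one day early would give 13 days and miss the window. A 28-day or early-termination positive needs a sample beyond the listed visits. The timing part of the concern is therefore correct.

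**2. Does the later sample count?**

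- Section 9.2 makes the independent second sample part of the endpoint definition and attaches it to no visit. Its window for a day-28 positive necessarily falls after the observation period.
- Section 5.1 excludes unscheduled data only where nothing else is specified. A definition that demands the second sample is such a specification. The opposite reading would make Section 9.2 ask for a sample and Section 5.1 discard it.
- Section 5.1.1.10 withholds a visit label. The inhibitor table in Section 9.2.4 is by drug and dose level, with the subject as unit, so it needs no label.
- Whether the retest is an unscheduled visit at all depends on the protocol, to which Section 9.2 refers for timing.

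**3. An initial positive without a valid retest**

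Section 9.2 requires confirmation. Without it the subject is not positive, so the rule is given. Section 5.2.2 does not settle whether such a subject has non-missing data for this table. The denominator has little influence:

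- If this is the only candidate in the low-dose cohort, the table shows 0 of 8 or 0 of 7. Both print as 0 with no percentage.
- If another subject in that cohort is confirmed, the choice is 1/8 = 12.5% or 1/7 = 14.3%.

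**4. Size of one subject**

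Cohort sizes are from Section 3.1: about 8 and about 10 enrolled, with additions so that "at least 6 subjects in the low-dose cohort and 8 subjects in the high-dose cohort provide evaluable PK and inhibitor data". The SAP plans no interval for this endpoint. The 95% level below is an assumption. The upper limit for 0/n is 1 − 0.025^(1/n); the limits for 1/n are exact (Clopper-Pearson).

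| n | Confirmed count 0: exact 95% upper limit | One subject in an unconfirmed row | Exact 95% limits for 1/n |
|---|---|---|---|
| 6 (minimum, low dose) | 45.9% | 1/6 = 16.7% | 0.4% to 64.1% |
| 8 (low dose; minimum, high dose) | 36.9% | 1/8 = 12.5% | 0.3% to 52.7% |
| 10 (high dose) | 30.8% | 1/10 = 10.0% | 0.3% to 44.5% |

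In each row the proportion 1/n lies well below the upper limit that goes with a zero count. At these sizes a zero does not rule out a rate of the order of one subject in the cohort.

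**The case for a change.** The strongest case for a change is that scheduling a retest does not settle how it is tabulated, and tabulation is the SAP's job. The general rules were written for single measurements at visits. Besides the Section 5.1 default, Section 5.1.1.10 keeps only the last evaluation when assessments repeat within a visit window, whereas this definition needs both results. Section 9.2.4 also reports by drug without saying which sample assigns the drug: a first positive at Visit 6, before BIVV001, might be confirmed only after it. Section 9.1 resolves a missing adverse-event start date towards counting the event, while an unconfirmed inhibitor goes the other way. Two sentences and one table row would close all this at almost no cost, in an open-label study where a rule fixed in advance is worth having.

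Part of this stands. An explicit sentence that confirmatory samples count whatever their visit label, with the event assigned to the first positive sample, would be tidier. It would, however, only write down what the definition already leads an analyst to do. Section 9.2 counts the retest window from the first positive, which makes that sample the natural date and drug assignment, and a definition that needs two results cannot be applied to the last one alone.

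The comparison with adverse events is weaker. There a date is missing and has to be inferred. Here confirmation was required on purpose, to keep single unverified results out of the count. The proposed row leaves the confirmed count as it is, so it corrects no number. It is a reasonable option for the table shells and carries its own cost: a false positive may be displayed in a primary safety table.

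**Conclusion.** No change to the plan follows. The dates are as described: a first positive at the 28-day visit can be confirmed only on days 42 to 56, after the last listed sample. The missing sentence is a detail that an analyst would supply in the intended sense, because the definition calls for the retest and the table is by subject. Counting an unconfirmed result as not positive is a direct consequence of the stated definition.

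The practical effect is confined to one summary table. The extra row would show one subject, 10.0% to 12.5% of a cohort at planned size or 12.5% to 16.7% at minimum evaluable size, beside an unchanged confirmed count. The subject's inhibitor status is listed, unscheduled data are listed too (Section 5.1), and the DSMC reviews safety listings as well as summaries (Section 3.5). The study tests no hypothesis (Section 3.2) and has about 18 subjects, so such a result would be easy to see in the listing.

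This conclusion assumes that Section 9.2 is read as the exception that Section 5.1 allows, and that the inhibitor listing shows the results behind each subject's status. How often the case would arise cannot be judged from the SAP.
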